### Statistical Methods:

The sample size has been selected in accordance with standard designs for Phase 1 assessments of PK, safety, and tolerability. The primary analysis will describe the PK characteristics of the two drug products. PK samples will be collected at pre-specified time points.

The PK parameters to be assessed include but are not limited to:

- Cmax maximum plasma concentration
- Cmin0-24 minimum plasma concentration from time zero to 24 hours post-dose
- tmax time of maximum plasma concentration
- λz terminal-phase rate constant
- t½ elimination half-life
- AUC0-24 area under the plasma concentration-time curve from time zero to 24 hours post-

	dosing
• $AUC_{0-t}$	area under the plasma concentration-time curve from time zero to time t (time of last quantifiable plasma concentration)
• $AUC_{0-\infty}$	area under the plasma concentration-time curve from time zero to infinity
• $CL/F$	apparent clearance
• $MRT$	mean residence time
• $V_z/F$	apparent volume of distribution

The secondary endpoints will describe the incidence of adverse events and laboratory abnormalities. Adverse events will be coded according to system organ class and preferred term using the Medical Dictionary for Regulatory Activities (MedDRA) (version 25.1 [released September 2022] or the current version). Their severity will be graded using the National Cancer Institute Common Terminology Criteria for Adverse Events (NCI CTCAE) 5.0 or the current version. Adverse events will be organized by system organ class and preferred term. The vital signs, ECG findings, and physical examination data and change of hematologic and chemistry parameters from baseline will be summarized for each post-baseline visit. Hematologic and chemistry parameters will be categorized as low, normal, or high based on laboratory normal ranges and presented as shifts from baseline. A detailed description of data analyses and statistical methods will be outlined separately in the Statistical Analysis Plan.
	
Date: 29 January 2025	

**Table 1: Schedule of Assessments**

Procedure	Period	Screening Period	Admission	Period 1						Period 2								End of Active Treatment		Follow Up Phone Call
	Visit	Screening	P1D-1	P1D1	P1D2	P1D3	P1D4	P1D5	P1D6	P2D-1	P2D1	P2D2	P2D3	P2D4	P2D5	P2D6	P2D7	Discharge	ET	Day 36 +/- 2 days
	Study Day	Days -21 to -1	-1	1	2	3	4	5	6	7	8	9	10	11	12	13	14	15	ET a	
Informed consent		X																		
Eligibility criteria review		X	X																	
Randomization				X																
Demographics b		X																		
Medical and surgical histories		X	X																	
Vital signs c		X	X	X	X	X	X	X	X	X	X	X	X	X	X	X	X	X	X	
Physical examination d		X			X							X						X	X	
Pregnancy test e		X	X															X	X	
Concomitant medications		X	X															X	X	
Adverse events				X	X	X	X	X	X	X	X	X	X	X	X	X	X	X	X	X
12-lead ECG f		X	X	X	X	X	X			X	X	X	X	X				X	X	
Hematology g		X	X		X					X		X						X	X	

Procedure	Period	Screening Period	Admission	Period 1						Period 2								End of Active Treatment		Follow Up Phone Call
	Visit	Screening	P1D-1	P1D1	P1D2	P1D3	P1D4	P1D5	P1D6	P2D-1	P2D1	P2D2	P2D3	P2D4	P2D5	P2D6	P2D7	Discharge	ET	Day 36 +/- 2 days
	Study Day	Days -21 to -1	-1	1	2	3	4	5	6	7	8	9	10	11	12	13	14	15	ET a	
Drug test (urine) alcohol test (breath)		X	X																	
Serology h		X																		
Serum chemistry and coagulation g		X	X		X					X		X						X	X	
Urinalysis g		X			X							X						X	X	
Admission to site			X																	
Study drug administration				X							X									
PK (plasma) i				X	X	X	X	X	X	X	X	X	X	X	X	X	X	X	X	
Discharge from site																		X	X	

Abbreviations: D = Day(s); ECG = electrocardiogram; ET = early termination; HbsAg = hepatitis B virus surface antigen; HCV = hepatitis C virus; HIV = human immunodeficiency virus; min = minute(s); PK = pharmacokinetics.

- a If participant withdraws from the study prematurely, the ET visit is to be conducted within 1 days after withdrawal. Day 36 Follow Up Phone Call is also required for ET subjects.
- b Includes participant's sex, age, race, and ethnicity, as permitted by local privacy regulations.
- c Vital signs include systolic (SBP) and diastolic blood pressure (DBP), pulse, respiration rate, and oral temperature (includes height, weight and BMI at the Screening Visit). Vital signs (except for height and weight) will be monitored periodically during and following study drug administration. Participant must be seated or in a supine position in a rested, calm state for at least 3 minutes before vital signs are collected. The following vital sign collection time points and windows are applicable during study drug administration days: Pre-dose (-60 min), and 0.25 (±5 min), 0.5 (±5 min), 1 (±10 min), 2 (±10 min), 4 (±10 min), 8 (±10 min), 12 (±10 min), 24 (±30 min), 48 (±30 min), 72 (±60 min), 96 (±60 min), 120 (±60 min), 144 (±60 min), and 168 (±60 min) hours post-dose. The 168-hour post dose P1D1 vitals may be combined with the pre-dose P2D1 timepoint, in which case, the P2D1 pre-dose vital signs should be collected within 60 minutes prior to dosing.
- d Physical examination will be complete at Screening and symptom-directed for all other study days at the PI's discretion. At a minimum, the complete physical examination should include general appearance, skin, head, ears, eyes, nose, and throat (HEENT), mouth/dental (if required), neck (including thyroid and nodes), cardiovascular, respiratory, gastrointestinal, and neurological. A symptom-directed physical examination will include assessment of any new participant complaints or changes from baseline

- as clinically indicated. A symptom-directed (or complete, based on the PI's discretion) physical examination should be completed 24 hours post-dose on Study Days 2 and 9.
- e Serum test at Screening, urine test at other time points; at Screening for post-menopausal participants, a blood sample will be tested for estradiol and follicle stimulating hormone to confirm post-menopausal status.
  - f Triplicate ECGs will be performed at screening, admission, dosing Day 1 in each period, and end of treatment (discharge or early termination). Triplicate ECGs will be measured at pre-dose (within -90min), and post dose 1hr ( $\pm 20$  min), 3hr ( $\pm 20$  min), 6hr ( $\pm 20$  min), 8hr ( $\pm 20$  min), 24 hr ( $\pm 60$  min), 48 hr ( $\pm 60$  min), and 72 hr ( $\pm 60$  min) post dose (for both doses) triplicates measurement will be taken within 5 minutes apart. Subjects should be at rest for 10 minutes prior to ECG. For participants that withdraw or are terminated early from the study, ECG will be performed at the ET visit.
  - g Samples must be collected following a minimum 8 hour fast.
  - h Serology includes HbsAg, anti-HCV Ab, and anti-HIV Ab.
  - i PK assessments should be performed on Day 1 of Periods 1 and 2 Pre-dose (hour 0) (within 60 mins prior to dosing), 0.5 hour (+/- 2 mins), 1 hour (+/- 5 mins), 2 hours (+/- 5 mins), 3 hours (+/- 10 mins), 4 hours (+/- 10 mins), 6 hours (+/- 10 mins), 8 hours (+/- 10 mins), 10 hours (+/- 10 mins), 12 hours (+/- 10 mins), 24 hours (+/- 60 mins), 48 hours (+/- 60 mins), 72 (+/- 60 mins), 96 (+/- 60 mins), 120 (+/- 60 mins), 144 ( $\pm 60$  min), and 168 hours (+/- 60 mins) relative to morning dose and at Discharge or ET visit at approximately the same time (+/- 1 hr) as the dose of study drug administration. The 168-hour post-dose P1D1 may be combined with the pre-dose PK collection for P2D1. P2D7 PK will be collected 144 ( $\pm 60$  min).

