#### **4.2. Participant Exclusion Criteria**

Participants meeting any of the following criteria are not eligible for study participation:

1. Any clinically significant underlying illness in the opinion of the Investigator.
2. Poor venous access.
3. Prior exposure to ARN-75039.
4. History of drug or alcohol abuse within 1 year of Screening in the opinion of the investigator, or a positive test for drugs of abuse or alcohol at Screening or Day -1.
5. Use of any prescription or over-the-counter (OTC) medications, including food supplements, vitamins, herbal medications (e.g., St. John's wort), and cannabis, with the exception of contraceptive medications and as needed (prn) acetaminophen or paracetamol (not exceeding 2 grams/day) within 7 days prior to study drug administration and through the Day 15 Discharge visit.
6. Any female who is pregnant or breastfeeding, or any female who is planning to become pregnant during the study and safety follow-up period.
7. Currently enrolled in another investigational device or drug study, or less than 30 days or 5 half-lives of the prior investigational agent (whichever is longer) or plans to enroll in another investigational device or drug study during the course of this study.
8. Inability to ingest all capsules of a multi-capsule dose within 5 minutes of ingestion of the first capsule.
9. Positive serology for hepatitis B virus (HBV), hepatitis C virus (HCV), or human immunodeficiency virus (HIV) at Screening; participants with adequately treated HCV are eligible for enrollment.
10. Consumption of Seville oranges, grapefruit or grapefruit juice within 72 hours prior to Day 1 or during the study.
11. History of malignancy, except adequately treated basal cell carcinoma or in situ carcinoma of the uterine cervix.

12. Smoking cigarettes, cigars, cigarillos or E-cigarettes
13. Any reason or condition that, in the investigator's opinion, may compromise study participation, present a safety risk to the participant, or may confound the interpretation of the study results.
14. A QT duration corrected for heart rate by Fridericia's formula (QTcF) > 450 millisecond (msec) based on either single or averaged QTcF values of triplicate ECGs obtained over a 3-minute interval (at Screening).
15. Blood product (including plasma) donation within 30 days before Screening.
16. Unwilling to consume a breakfast on study drug administration days.
17. History of:

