## 7.9. Pharmacokinetic Analyses

Plasma ARN-75039 concentrations will be determined at all pre- and post-dose time points.

The following PK parameters will be computed at minimum from plasma concentration data:

$C_{\max}$	maximum plasma concentration
$t_{\max}$	time of maximum plasma concentration
$\lambda_z$	terminal-phase rate constant
$t_{1/2}$	elimination half-life
$AUC_{0-24}$	area under the plasma concentration-time curve from time zero to 24 hours post-dosing
$AUC_{0-t}$	area under the plasma concentration-time curve from time zero to time t (time of last quantifiable plasma concentration)
$AUC_{0-\infty}$	area under the plasma concentration-time curve from time zero to infinity
$CL/F$	apparent clearance
$MRT$	mean residence time
$V_z/F$	apparent volume of distribution

Plasma ARN-75039 concentrations and non-compartmental PK parameters will be tabulated by treatment using descriptive statistics. Individual elapsed sampling times will be used in the PK analysis. The  $C_{\max}$  and  $t_{\max}$  will be obtained directly from the experimental observations and  $AUC_{0-t}$  will be calculated using the linear trapezoidal rule.

Individual concentration-time data will be listed and displayed graphically on the linear and semilogarithmic scales. The concentration-time data will be summarized descriptively in tabular and graphical format (linear and semilogarithmic scale).

Additional details regarding PK analyses will be documented in a formal Statistical Analysis Plan.

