2.3 Endpoints

Primary:

- Relative bioavailability comparison of 300 mg neat ARN-75039 in HPMC capsules (Treatment A; reference) to 300 mg ARN-75039 with excipients tablets (Treatment B; comparator) following oral administration under fed conditions.
- PK parameters of 300 mg ARN-75039 with excipients tablets and 300 mg neat ARN-75039 in HPMC capsules, including but not limited to:
 - Area under the plasma concentration-time curve from time zero to time of last quantifiable concentration (AUC_{0-t}).
 - Area under the plasma concentration-time curve from time zero to 24 hours post-dose (AUC_{0-24}).
 - Area under plasma concentration-time curve from time zero to infinity ($AUC_{0-\infty}$).
 - Maximum observed plasma concentration (C_{max}).

- Minimum observed plasma concentration from time zero to 24 hours post-dose $C_{min0-24}$.
- Time to reach C_{max} (t_{max}).
- Half-life ($t_{1/2}$).
- Apparent clearance after extravascular administration (CL/F).
- Apparent volume of distribution during the terminal phase after extravascular administration (V_z/F).

Secondary:

- Type and frequency of treatment-emergent adverse events (TEAEs).
- Type and frequency of treatment-emergent serious adverse events (TESAEs).
- Type and frequency of study drug-related >Grade 1 TEAEs.
- Type and frequency of changes in clinical laboratory values, ECGs, colonic transit time (biomarker), physical examinations, and vital signs.

3 Study Design and Methods

ARN-75039-103 is a comparative, randomized, single-dose, crossover study to assess the PK, safety, and tolerability of neat ARN-75039 in hydroxypropyl methylcellulose (HPMC) capsules against ARN-75039 with excipients in tablet form administered by the oral route in healthy adult participants. The safety assessments will include assessments of vital signs, clinical laboratory values, and ECGs.

A total of 16 participants were randomized 1:1 into one of the following two sequences:

Sequence 1:

[figure not shown]
- Period 1: 300 mg neat ARN-75039 in HPMC capsules (Treatment A; reference product)
- Period 2: 300 mg ARN-75039 with excipients in tablet form (Treatment B; comparator)

Sequence 2:

- Period 1: 300 mg ARN-75039 with excipients in tablet form (Treatment B; comparator)
- Period 2: 300 mg neat ARN-75039 in HPMC capsules (Treatment A; reference product)

A study scheme is provided below:

Sequence 1

Sequence 2

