3.1 Study Assessments

3.1.1 Pharmacokinetic Assessments

The primary pharmacokinetic assessments are based on ARN-75039 plasma concentrations.

Fifteen venous blood samples will be withdrawn via an indwelling cannula or by venipuncture at regular time intervals. The exact date and time of PK sample collection is to be documented in eCRF. Blood samples will be collected prior to and following administration of the single oral dose of neat ARN-75039 in HPMC capsules or ARN-75039 with excipients in tablet form at according to the timepoints listed in the SOA (Table 1).

The actual sampling time will be used for estimating PK parameters.

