4.6 Pharmacokinetic Analysis

Pharmacokinetic analyses will be performed for each participant in the PK population. Blood samples will be collected and resulting plasma analyzed to obtain plasma concentrations. The plasma concentration data will be listed at actual and nominal time points by participant. Plasma concentrations will be summarized by treatment at each nominal time point of plasma collection using descriptive statistics (n, mean, SD, CV%, geometric mean, geometric CV%, median, min, and max values), and listed by participant, treatment, sequence and with both nominal and actual plasma collection point.

For plasma concentration data, all values below the quantification limit (BQL) will be labeled as such in the concentration listings and treated as zero for the concentration data summary statistics and mean summary figures.

For PK parameter calculations, concentrations BQL will be set to zero if they occur prior to the first quantifiable concentration and after the last quantifiable concentration. The BQL values in between measurable plasma concentrations will be set to missing.

The plasma PK parameters for ARN-75039 will be estimated by non-compartmental analysis (NCA) methods using Phoenix WinNonlin (version 8.1 or higher, Certara USA Inc., Princeton, NJ, USA) and will be based on actual individual time since dosing of blood sample collection.

The following PK parameters will be computed at minimum from plasma concentration data:

C_{\max}	maximum plasma concentration
$C_{\min 0-24}$	observed plasma concentration from time zero to 24 hours post-dose
t_{\max}	time of maximum plasma concentration
$\lambda_z (k_{el})$	terminal-phase rate constant
$t_{1/2}$	elimination half-life
AUC_{0-24}	area under the plasma concentration-time curve from time zero to 24 hours post-dosing
AUC_{0-t}	area under the plasma concentration-time curve from time zero to time t (time of last quantifiable plasma concentration)

$AUC_{0-\infty}$	area under the plasma concentration-time curve from time zero to infinity
CL/F	apparent clearance
MRT	mean residence time
V_z/F	apparent volume of distribution

The C_{max} and t_{max} will be obtained directly from the experimental observations and AUC_{0-t} will be estimated using the Linear up – Log down trapezoidal method from time 0 hour to last observed concentration hour.

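### As written, the primary endpoint Cmin0-24 does not reliably give a 24-hour trough: the rules can select the pre-dose sample, the 0.5-hour sample, or a sample that depends on whether the 24-hour draw was taken before or after 24:00

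*Protocol*

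**What the plan says.** - **Endpoint.** Cmin0-24 is listed among the primary endpoints in the Protocol synopsis and in SAP 2.3, where it is the "Minimum observed plasma concentration from time zero to 24 hours post-dose". SAP 4.6 lists the parameter but leaves out the word minimum. Protocol 7.9 does not list it, and Protocol section 2 prints its symbol as Cmax0-24.
- **Sampling.** Protocol Table 1, footnote i (repeated in SAP Table 1) starts each profile with "Pre-dose (hour 0) (within 60 mins prior to dosing), 0.5 hour (+/- 2 mins" and later gives "12 hours (+/- 10 mins), 24 hours (+/- 60 mins".
- **Time basis.** Protocol 7.9: "Individual elapsed sampling times will be used in the PK analysis". SAP 3.1.1: "The actual sampling time will be used for estimating PK parameters". SAP 4.6 says the non-compartmental parameters "will be based on actual individual time since dosing of blood sample collection".
- **Values below quantification.** SAP 4.6: "For PK parameter calculations, concentrations BQL will be set to zero if they occur prior to the first quantifiable concentration".
- **Pre-dose levels.** Protocol 4.2 excludes anyone with "Prior exposure to ARN-75039". SAP 4.1 lists a profile whose pre-dose value exceeds 5% of its own Cmax but leaves it out of the summaries.
- **Use of the endpoint.** SAP 4.6 summarises PK parameters by treatment, including geometric mean and geometric CV%. Its ANOVA, 90% confidence intervals and 80.00-125.00% limits cover Cmax, AUC0-t and AUC0-∞ only.

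Neither document says whether the pre-dose and absorption-phase samples belong to the Cmin0-24 interval, or whether an in-window draw after 24.0 hours does. SAP 4.6 names a trapezoidal method for AUC0-t, but no rule for ending AUC0-24 at exactly 24.0 hours.

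**The concern.** A minimum over 0-24 hours is presumably meant to describe the trough before a next daily dose. After a single dose, however, concentrations are low at both ends of that interval, so the minimum can come from either end. At the early end it may be the pre-dose zero or a rising concentration soon after dosing. At the late end, half of the permitted 24-hour window lies past 24.0 hours. By actual time, such a draw falls outside the stated interval although it is fully compliant.

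At stake is the meaning of a named primary endpoint in a study whose primary objective is to compare two formulations. Its by-treatment summary could consist of zeros, describe early absorption, or mix sampling times according to when blood was drawn.

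**Working it through.** The documents give no figure for this point to reproduce, and the 16 participants were not derived statistically. The check asks which scheduled sample is the minimum under each possible reading.

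**How often the boundary matters.** Sixteen participants give 32 profiles. If 25%, 50% or 75% of 24-hour draws are taken after 24:00 (assumed), 8, 16 or 24 profiles are affected.

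**Reading (a): hour 0 included.** With no earlier exposure, the Period 1 pre-dose value should be below quantification and is set to zero, so Cmin0-24 = 0 whenever the 24-hour sample is drawn. A zero has no logarithm, so the planned geometric statistics fail. In Period 2, profiles kept in the summaries have pre-dose ≤ 5% of Cmax. Mean C24/Cmax in Protocol Table 2 (dogs) is:
- capsule: 369.1/4518 = 8.2%
- prototype 1 tablet: 335.6/5105 = 6.6%
- prototype 5 tablet: 399/5346 = 7.5%

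On those figures pre-dose is again the minimum.

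**Reading (b): pre-dose excluded, all post-dose samples count.** The human half-life and tmax are not given, so ranges are assumed: half-life 5.3, 12, 24, 48 and 72 h; tmax 2, 3, 4, 5 and 6 h (25 combinations). The 5.3 h value reflects the dog table: (24 − tmax)·ln 2 / ln(Cmax/C24) = 5.26, 5.60 and 5.34 h for the three products. The model is one-compartment oral, C(t) ∝ exp(−ke·t) − exp(−ka·t), with ke = ln 2 / t½ and ka solved from ln(ka/ke)/(ka − ke) = tmax.

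In 16 of 25 combinations the 0.5 h sample is the minimum whether or not the 24 h draw counts. In the other 9 the 24 h sample is the minimum, and losing it changes the selected sample (concentrations as fractions of Cmax):

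| t½ (h) | tmax (h) | C0.5 | C12 | C24 | Minimum moves to | Ratio to C24 |
|---|---|---|---|---|---|---|
| 5.3 | 2 | 0.588 | 0.302 | 0.063 | 12 h | 4.8 |
| 5.3 | 3 | 0.413 | 0.381 | 0.079 | 12 h | 4.8 |
| 5.3 | 4 | 0.313 | 0.492 | 0.105 | 0.5 h | 3.0 |
| 5.3 | 5 | 0.251 | 0.621 | 0.148 | 0.5 h | 1.7 |
| 12 | 2 | 0.648 | 0.580 | 0.290 | 12 h | 2.0 |
| 12 | 3 | 0.465 | 0.631 | 0.315 | 0.5 h | 1.5 |
| 12 | 4 | 0.354 | 0.689 | 0.345 | 0.5 h | 1.03 |
| 24 | 2 | 0.700 | 0.759 | 0.537 | 0.5 h | 1.3 |
| 48 | 2 | 0.747 | 0.870 | 0.732 | 0.5 h | 1.02 |

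That is 6 moves to 0.5 h and 3 to 12 h.

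**Reading (c): only post-peak samples count.** A lost 24 h draw is then always replaced by the 12 h draw. With log-linear decline, C12/C24 = 2^(12/t½). If half the draws are late, the geometric mean is multiplied by the square root of that ratio, 2^(6/t½):

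| t½ (h) | C12/C24 | Geometric mean overstated by |
|---|---|---|
| 12 | 2.00 | 41% |
| 24 | 1.41 | 19% |
| 48 | 1.19 | 9% |
| 72 | 1.12 | 6% |

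**After the fix.** With the scheduled 24 h sample always used, a draw 60 minutes late changes the value by 2^(−1/t½) − 1: −5.6% at 12 h, −2.8% at 24 h and −1.0% at 72 h (−12.3% at 5.3 h). The sample no longer switches.

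**The case against.** The strongest reply is that no sentence discards a compliant 24-hour sample. Concentration summaries use nominal times, and the dog tables label the analogous column as Cmin at 24 hours, so C24 is probably what is meant. That is likely the intent. It is not written down, however, and the actual-time statements in both documents point the other way for parameter derivation.

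A second reply is that late draws often do not matter. Protocol 6.4 and SAP 4.7.6 place approximate Cmax at 3-6 hours. For tmax of 3 to 6 h and half-lives of 12 to 72 h, 14 of the 16 model combinations give the 0.5-hour sample either way, 2 move to 0.5 h, and none moves to 12 h. This stands, but it shows that the written definition usually returns an early absorption value, which is not a trough.

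Two stronger readings are tempting and are not supported:
- A reader might infer that Cmin0-24 is in general a mixture of 12-hour and 24-hour values, with the 6% to 41% bias. That needs a rule limiting the minimum to post-peak samples, which neither document states. Without it, the move to 12 h appears in only 3 of 25 combinations, all with half-lives of 12 h or less, whereas Protocol 3.2 calls the half-life long.
- A reader might infer a wider confidence interval for the tablet/capsule ratio. SAP 4.6 plans no such interval for Cmin0-24.

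**Conclusion.** The point holds as a defect of definition. Under the written rules, Cmin0-24 is the pre-dose value (expected zero in Period 1), often the 0.5-hour value, or a value that changes sample when a compliant draw falls after 24:00. The overstatement of about 6% to 41% applies only to the post-peak reading, with half of draws late and half-lives of 72 down to 12 h, all assumed. A long half-life favours the lower end. The sample counts in reading (b) rest on a one-compartment model and assumed ranges of half-life and tmax.

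The consequence is confined to the by-treatment descriptive summaries. The ANOVA and the 80.00-125.00% criterion do not use Cmin0-24, so the relative bioavailability conclusion is untouched. It still merits correction, because the endpoint is named as primary and the repair is nearly free.

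**What to change.** In SAP 4.6:
- Define Cmin0-24 as the concentration in the scheduled 24-hour post-dose sample when that sample is within its window, whatever its actual time. State that pre-dose and absorption-phase samples are not used, and list the actual time.
- State that AUC0-24 is interpolated to exactly 24.0 hours.

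The cost is about two sentences, with no new samples or visits. The rule can be applied to blood already drawn, which matters because SAP section 3 describes randomisation in the past tense. Narrowing the 24-hour window is unnecessary and would not cure the problem alone: a draw at 24:05 would still lie outside the interval. Once the scheduled sample is used, a full hour's delay changes the value by only 1.0% to 5.6% for half-lives of 72 to 12 h.
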